2.1. Modifications to the Analysis Plan Described in the Protocol

None.

[figure not shown]
2.2. Study Objectives, Endpoints, and Estimands

The following are the objectives and endpoints in this study. Estimand framework will not be applied to this Phase 1 study in healthy participants.

Objectives	Endpoints
Primary:	Primary:

 • To estimate the effect of multiple doses of itraconazole 200 mg QD on the PK of PF-07817883 following a single oral dose of PF-07817883 300 mg 	
 • PF-07817883 plasma PK parameters: C_{max} and AUC_{inf} (if data permits, otherwise AUC_{last}) with itraconazole (test) versus without itraconazole (reference)
Secondary:	Secondary:

 • To evaluate the safety and tolerability of PF-07817883 in healthy participants in the absence and presence of multiple doses of itraconazole • To characterize additional PK parameters of PF-07817883 when administered alone or with itraconazole in healthy participants 	
 • Assessment of TEAEs, clinical laboratory abnormalities, vital signs, physical exams, and 12-lead ECGs • PF-07817883 plasma PK parameters: T_{max}, and if data permits, $t_{1/2}$, CL/F, V_z/F, with and without coadministration of itraconazole
Tertiary/Exploratory:	Tertiary/Exploratory:

 • To assess the similarity of PK in blood by microsampling technique(s) with those in plasma by venipuncture • To characterize additional PK parameters of PF-07817883 following a single oral dose of PF-07817883 with and without itraconazole by renal function • To evaluate the drug-product acceptability of PF-07817883 	
 • Concentration of PF-07817883 in blood and plasma as well as PF-07817883 plasma PK parameters: AUC_{12}, C_{max} • Concentration of PF-07817883 in urine and urine PF-07817883 PK parameters: Ae_{24}, CL_R, if applicable and as data permits • Score on a 14-item drug-product acceptability questionnaire

2.3. Study Design

This is a Phase 1, open label, 2-period, fixed sequence study to estimate the effect of the strong CYP3A4 inhibitor, itraconazole, on the plasma and urine (if applicable) PK of PF-07817883 in healthy adult participants. The study will consist of 2 treatments: a single oral dose of PF-07817883 300 mg alone and a single oral dose of PF-07817883 300 mg in combination with multiple doses of itraconazole 200 mg QD. A total of approximately 12 healthy adults will be enrolled into the study to ensure at least 10 participants complete the study. The treatment will consist of a single fixed sequence. Participants who discontinue from the study for non-safety reasons may be replaced at the sponsor's discretion in collaboration with the investigator.

Figure 1. Study Schema

3.2. Secondary Endpoints

The secondary endpoints include the overall safety profile of a single dose of PF-07817883 alone and with multiple doses of itraconazole, as characterized by adverse events, laboratory tests, vital signs, physical exams, and 12-lead ECGs (discussed in [Section 3.5](#)).

Other secondary endpoints are additional plasma PK parameters (including T_{max} , $t_{1/2}$, CL/F and V_z/F , defined in Table 2) of PF-07817883 (following a single dose administration of PF-07817883 alone and with multiple doses of itraconazole).

3.3. Other Endpoints

3.3.1. Exploratory PK Endpoints

Blood (by microsampling using the Tasso® M20 device) and urine samples for urine PK analysis of PF-07817883 will be taken according to the SoA given in the protocol. For each individual, a blood to plasma (B/P) ratio will be calculated by dividing concurrent (i.e. Day 1, 1 hour post-dose) whole blood PF-07817883 concentration with the plasma PF-07817883 concentration. A geometric mean and CV% of the B/P ratio from all individuals will also be calculated. The plasma equivalent PF-07817883 concentration by microsampling will be calculated by dividing with the individual B/P ratio. As a sensitivity analysis, the plasma

equivalent concentration will also be calculated using the geometric mean B/P ratio from all individuals. AUC₁₂ and C_{max} will be derived from blood samples collected using the Tasso® M20 device, and then adjusted for B/P ratio. Concentration of PF-07817883 in urine will be analyzed and additional urine PK parameters defined in Table 3 will be derived.

Table 3. Urine PF-07817883 PK parameter definitions

Parameter	Definition	Method of Determination
Ae_{24}	Total amount of unchanged drug excreted in the urine over 24 hours	Sum of amount excreted for each collection period.
$Ae_{24\%}$	Total amount of unchanged drug excreted in the urine over 24 hours, expressed as percent of dose	$100 \times (Ae_{24}/Dose)$
CL_R	Renal clearance	Ae_{24}/AUC_{24}

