**Table 2. Period 1 (PF-07817883 Alone): Detailed Sampling Schedule**

Visit Identifier	Treatment Period 1										Notes		
Period 1 Day	1					2	3	4	5	Study Day 5 is Period 1 Day 5 and Period 2 Day 1.			
Study Day	1					2	3	4	5				
Hours Relative to Dosing at 0 h	0	0.5	1	1.5	2	4	6	8	12	24	48	72	96
PF-07817883 administration	X												
PK blood sampling for PF-07817883	X	X	X	X	X	X	X	X	X	X	X	X	
PK micro-sampling (Tasso® M20) for PF-07817883		X	X		X		X						
Blood/plasma ratio sample for PF-07817883			X										
PK urine collection for PF-07817883	X	→	→	→	→	→	→	→	→	X			

The sample at 0 h will be the pre-dose PK blood sample.  
 The sample on Study Day 5 should be collected before dosing of itraconazole of Period 2.

For details refer to Lab Manual.

The sample at 0 h will be the pre-dose urine sample. Urine collection will continue up to 24 hours post-dose.  
 See Section 8.5.2.

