5.3.2. PK Parameters

Actual PK sampling times will be used in the derivation of PK parameters. If a PK parameter cannot be derived from a participant’s concentration data, the parameter will be coded as NC (i.e., not calculated). (Note that NC values will not be generated beyond the day that a participant discontinues). In summary tables, statistics will be calculated by setting NC values to missing; and statistics will be presented for a particular treatment with ≥ 3 evaluable measurements. PK parameter analyses will not be performed for a particular parameter if more than 50% of the data are NC.

If an individual participant has a known biased estimate of a PK parameter (due for example to an unexpected event such as vomiting before all the compound is adequately absorbed from the gastrointestinal tract), this will be footnoted in summary tables and will not be included in the calculation of summary statistics or statistical analyses.

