6.2.3. Other Endpoints – Exploratory PK Endpoints

AUC₁₂ and C_{max} derived from blood samples collected using the Tasso® M20 device adjusted for B/P ratio will be summarized for PF-07817883 (administered alone in Period 1) and will include the set of summary statistics as specified in [Table 4](#). Summary statistics of the whole blood concentrations, plasma equivalent concentrations by microsampling using individual B/P ratio and plasma equivalent concentrations by microsampling using geometric mean B/P ratio at nominal time of collection as defined in SoA will be calculated.

Furthermore, to determine correlation in concentrations derived from time matched Tasso® M20 microsampling (calculated using individual or population) and traditional venous plasma sampling, Bland-Altman plot analysis will be performed to evaluate the bias and SD of the bias between the mean differences and to estimate an agreement interval within a 95% confidence limit. A concentration correlation analysis will be conducted with the same dataset.

In addition, Ae₂₄, Ae_{24%} and CL_R, derived from PF-07817883 concentrations measured from urine samples collected (if analyzed) will be summarized by treatment and will include the set of summary statistics as specified in [Table 4](#).

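### Microsampling agreement (minor, exploratory): with individual B/P ratios the 1 h pair tests device blood against venous whole blood, not plasma; and device AUC12 cannot be formed by trapezoid if device sampling ends at 6 h

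*SAP*

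**What the plan says.** SAP 3.3.1 defines one blood-to-plasma (B/P) ratio per participant, obtained by "dividing concurrent (i.e. Day 1, 1 hour post-dose) whole blood PF-07817883 concentration with the plasma PF-07817883 concentration". The device (Tasso M20) results are then converted: "The plasma equivalent PF-07817883 concentration by microsampling will be calculated by dividing with the individual B/P ratio". As a sensitivity analysis the "equivalent concentration will also be calculated using the geometric mean B/P ratio from all individuals". Protocol 8.5.1 takes the whole blood for the ratio as a 0.1 mL aliquot of the PK blood sample before centrifugation, so it comes from the venous tube.

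SAP 6.2.3 plans the agreement analysis: for "time matched Tasso® M20 microsampling (calculated using individual or population) and traditional venous plasma sampling, Bland-Altman plot analysis will be performed". It adds: "A concentration correlation analysis will be conducted with the same dataset". It does not set the 1 h time point apart, and it does not state the scale of the differences.

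For the device, SAP 3.3.1 also plans AUC12 and Cmax, which "will be derived from blood samples collected using the Tasso® M20 device, and then adjusted for B/P ratio". SAP Table 2 defines AUC12 over 0 to 12 h by the linear/log trapezoidal method and gives no extrapolation rule for it. SAP 5.3.2 codes a parameter that cannot be derived as NC and drops the analysis of a parameter when more than half its values are NC. In Protocol Table 2, the row "PK micro-sampling (Tasso® M20) for PF-07817883" reads in the extracted text as marked at 0.5, 1, 2 and 6 h only.

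**The concern.** The exploratory objective in Protocol 3 is to show that PK by microsampling resembles PK in venous plasma. A pair in which the plasma result appears on both sides cannot contribute to that. It cannot reveal disagreement with plasma at that time, yet it is pooled with pairs that can. In the correlation analysis the 1 h plasma value sits on both axes.

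The AUC12 question is whether the schedule can deliver the parameter at all. Every participant has the same device times, so if AUC12 cannot be derived for one it cannot be derived for any.

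The stakes are limited. This is an exploratory endpoint from Period 1 only. It matters because Protocol 4.2 ties acceptable concordance to using microsampling in future studies.

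**Working it through.** **Part 1: the 1 h pair**

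Notation: T_j is device blood at time j, W1 is venous whole blood at 1 h, and P_j is venous plasma at time j. P1 is taken to be the 1 h PK plasma result. This is a reading of the documents: the aliquot comes from the PK tube, and one venous PK sample is scheduled at 1 h.

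- Individual ratio: W1 / P1. Plasma-equivalent at time j: T_j × P1 / W1.
- At 1 h, log scale: log(T1 × P1 / W1) − log(P1) = log(T1 / W1). Plasma cancels exactly.
- At 1 h, difference scale: T1 × P1 / W1 − P1 = P1 × (T1 / W1 − 1). Plasma remains only as a multiplier, and the difference is zero only if T1 = W1.

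The documents give no error sizes, so the log-scale SDs below are assumptions: t (device), w (whole blood), p (plasma), with independent errors unless stated.

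- Variance at 1 h: t² + w². At other times: t² + w² + 2p².
- All SDs 0.1: SD ratio √(0.02 / 0.04) = 0.71. Pooled over four times: √[(3 × 0.04 + 0.02) / 4 / 0.04] = √(0.035 / 0.04) = 0.935. The limits are about 6% narrower than with an independent 1 h plasma value.
- t = 0.15, w = 0.10, p = 0.05: SD ratio √(0.0325 / 0.0375) = 0.93. Pooled: √(0.03625 / 0.0375) = 0.983, under 2% narrower.
- If W1 and P1 errors from the shared tube correlate by ρ, the variance at other times falls by 2ρwp. With all SDs 0.1 the SD ratio is 0.82 at ρ = 0.5 and 0.91 at ρ = 0.8.
- Correlation, all SDs 0.1 and between-participant log-SD 0.3: at 1 h, (0.09 + 0.01) / √(0.12 × 0.10) = 0.91; at other times, 0.09 / √(0.12 × 0.10) = 0.82. The pooled correlation changes by at most 0.02.
- Geometric-mean version, n participants: variance t² + p² + (w² + p²)/n at other times, less 2p²/n at 1 h. All SDs 0.1 and n = 12: √(0.0200 / 0.0217) = 0.96. Across the assumed SDs and n = 10 or 12 the range is 0.92 to 0.99, so little of the problem remains.

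On absolute differences the answer depends on the profile. In simulation (12 participants, all SDs 0.1, five assumed mean profiles) the pooled limits were 7% to 14% narrower than with an independent 1 h plasma value. Dropping the 1 h pair changed the pooled SD by −7% to +6%. On the log scale the same step gives 1 / 0.935 = 1.07, a rise of 7%.

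**Part 2: device AUC12**

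- The hours row of Protocol Table 2 has 13 times. The device row has 13 cells, marked at 0.5, 1, 2 and 6 h.
- Two other rows support the alignment: the B/P mark falls at 1 h, as the SAP says, and urine runs from 0 to 24 h, as Protocol 4.1 says.
- One row counts against relying on the extraction: venous PK shows 12 marks, although Protocol 4.1 has sampling to 96 h. A mark has been lost there.

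If device sampling does end at 6 h, the trapezoid yields at most AUC0-6, with time zero set to 0. The part left out, for an assumed one-compartment oral profile, is 1 − A(6)/A(12), where A(T) is proportional to (1 − e^(−ke·T))/ke − (1 − e^(−ka·T))/ka. With half-life 3 h and ka 1/h this is 1 − 2.249/3.058 = 26.5%. For ka of 1 to 2/h the missing share is:

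| Assumed half-life | Share of AUC12 in 6-12 h |
|---|---|
| 1.5 h | 8-11% |
| 3 h | 23-27% |
| 6 h | 36-39% |
| 12 h | 44-47% |

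If the gap were instead filled by extrapolating from the 2 and 6 h values, an error-free device would give 99% to 109% of venous AUC12 for 29 of 30 assumed one-compartment profiles (the other still rises from 2 to 6 h), and 91% to 101% for 90 assumed biexponential profiles. Cmax from the four times would be 92% to 100% of the venous value.

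**The case against.** The plan already contains most of the remedy for part 1: the geometric-mean conversion is specified, and SAP 6.2.3 provides for either ratio. The excess variance lost at 1 h is plasma assay error alone (with no tube correlation), and Protocol 8.5.1 requires a validated plasma method, so equal error SDs may overstate the effect. Even the 6% figure is small beside sampling error: in simulation with 12 participants and four pairs each, the pooled SD has a CV of about 13%, rising to about 15% without the 1 h pair. No numeric threshold for acceptable concordance is given, so no decision is shown to change. The 1 h pair is also informative in its own right, as a comparison of device with venous whole blood. All of this stands and is why the point is minor. None of it makes the 1 h pair a test against plasma.

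On part 2, the table has demonstrably lost a mark elsewhere, parameters are derived only as data permit, and NC is a stated outcome. SAP 6.2.3 only summarizes device AUC12 and Cmax; the planned agreement analysis uses concentrations. That stands too, so the point remains conditional. Protocol 4.2 says the microsamples would allow AUC calculation, but it does not name 12 h or supply a rule for 6 to 12 h.

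A reader might infer that the whole agreement analysis is circular, or that its limits are materially too narrow. The documents do not support that: three of four pairs per participant are genuine comparisons with plasma, and a second version is planned. A reader might also infer that the plan builds in a bias of up to 9% in device AUC12. That would need an extrapolation the SAP does not specify and a side-by-side reading it does not plan.

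**Conclusion.** Both parts hold as minor, exploratory points.

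1. In the individual-ratio version, one pair in four compares device blood with venous whole blood. This is exact algebra once P1 is read as the 1 h PK plasma result. Its effect on pooled limits is small: about 6% on the log scale with equal error SDs, under 2% in the more precise plasma case above, and dependent on the profile on the absolute scale. The geometric-mean version largely avoids it.
2. If device sampling ends at 6 h, AUC12 as defined cannot be formed for the device. It would be NC for every participant or rest on a rule that neither document states. This depends on confirming Protocol Table 2; if there is a 12 h device sample, this part falls away.

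The error SDs and PK profiles used for size are assumptions. The primary interaction estimates and the safety results are not affected.

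**What to change.** **Agreement analysis (SAP 6.2.3).** Run the individual-ratio Bland-Altman and correlation analyses on the log or percent scale, without the 1 h pair. The scale should be stated, because on absolute differences removing that pair can move the SD either way. Report the 1 h pair separately, labelled as device versus venous whole blood. Keep the geometric-mean version beside it with all four times.

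**Device AUC12 (SAP 3.3.1 and 6.2.3).** Confirm the device times in the source table. If they end at 6 h, use AUC0-6 and Cmax as the similarity comparison, deriving both for device and venous plasma from the same four times (0.5, 1, 2 and 6 h) with the same time-zero convention. Report device AUC12 only if it is labelled as extrapolated from 6 to 12 h, and otherwise as NC.

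**Cost.** SAP wording, an entry in SAP 2.1 (which now lists no modifications), and a little programming. No sample is added. Protocol 9 calls for an amendment only for major changes to the primary endpoints or their analyses. The downsides are that the individual-ratio analysis keeps 36 of 48 pairs with 12 participants (30 of 40 with 10), 1 h agreement with plasma is then seen only in the geometric-mean version, and the matched AUC covers 0 to 6 h instead of 0 to 12 h.

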3.3.2. Drug-Product Acceptability

Drug product acceptability will be assessed based on participants' responses to a sponsor-provided 14-item questionnaire. Each item will be evaluated on a Likert scale with numeric categories to capture the level of agreement or disagreement with a statement about drug-product appearance, palatability, swallowability, or overall impression of taking the drug product (1=strongly agree, 5=strongly disagree).

3.4. Baseline Variables

Baseline characteristics will be collected according to the schedule of activities (SoA) as specified in the protocol.

3.5. Safety Endpoints

The following data will be considered in standard safety summaries (see protocol for collection days, baseline assessment, and list of parameters):

- Adverse events (AE)
- Laboratory data
- Vital signs data
- ECG results

3.5.1. Adverse Events

Any adverse events occurring following start of treatment will be considered as treatment emergent adverse event (TEAE). Events that occur during follow-up within the lag time of up to 35 days after the last dose of study intervention will be counted as treatment emergent and attributed to the last treatment taken. Events that occur during the washout period between study periods will be counted as treatment emergent and attributed to the previous treatment taken. The time period for collecting AEs ("active collection period") for each participant begins from the time the participant provides informed consent.

3.5.2. Laboratory Data

Safety laboratory tests will be performed as described in the protocol. To determine if there are any clinically significant laboratory abnormalities, the haematological, clinical chemistry (serum) and urinalysis safety tests will be assessed against the criteria specified in the sponsor reporting standards. The assessment will not take into account whether each participant's baseline test result is within or outside the laboratory reference range for the particular laboratory parameter.

For both periods, the baseline measurement is the last predose measurement prior to administration of PF-07817883 in each study period. Changes from baseline will be defined as the change between the postdose and baseline measurements.

3.5.3. Vital Signs

Supine blood pressure (BP), pulse rate (PR) and respiratory rate will be measured at times specified in the SoA given in the protocol.

For both periods, the baseline measurement is the last predose measurement prior to administration of PF-07817883 in each study period. Changes from baseline will be defined as the change between the postdose and baseline measurements.

3.5.4. Electrocardiograms

QT interval, QTcF, PR interval, QRS and heart rate (HR) will be recorded at each assessment time indicated in the SoA given in the protocol. If not supplied, QTcF will be derived using Fridericia's heart rate correction formula:

$$QTcF = QT / (RR)^{(1/3)} \text{ where } RR = 60/HR \text{ (if not provided)}$$

For both periods, the baseline measurement is the last predose measurement prior to administration of PF-07817883 in Period 1. Changes from baseline will be defined as the change between the postdose ECG measurement and the baseline ECG.

The maximum absolute value (postdose) and the maximum increase from baseline for QTcF, PR interval and QRS, over all measurements taken postdose, will be determined.

The maximum increase from baseline will be calculated by first subtracting the baseline value from each postdose measurement to give the change from baseline. The maximum of these values over the respective period will then be selected, except in the case where a participant does not show an increase. In such an instance, the minimum decrease should be taken.

4. ANALYSIS SETS (POPULATIONS FOR ANALYSIS)

Data for all participants will be assessed to determine if participants meet the criteria for inclusion in each analysis population prior to releasing the database and classifications will be documented per standard operating procedures.

Participant Analysis Set	Description
Enrolled	"Enrolled" means a participant's, or their legally authorized representative's, agreement to participate in a clinical study following completion of the informed consent process and assignment to study intervention. Potential participants who are screened for the purpose of determining eligibility for the study, but do not participate in the study, are not considered enrolled, unless otherwise specified by the protocol. A participant will be considered enrolled if the informed consent is not withdrawn prior to participating in any study activity.
Safety Analysis Set	All participants enrolled and who take at least 1 dose of study intervention.
PK Concentration Set	All participants who take at least 1 dose of study intervention and in whom at least 1 concentration value is reported.
PK Parameter Set	All participants who take at least 1 dose of study intervention and in whom at least 1 of the PK parameters of primary interest are reported.

5. GENERAL METHODOLOGY AND CONVENTIONS

Final analysis will be performed after study participant data set release following last participant last visit.

5.1. Hypotheses and Decision Rules

No statistical hypothesis will be tested in this study.

5.2. General Methods

5.2.1. Analyses for Binary/Categorical Endpoints

For binary or categorical variables, number of participants, numbers and percentages of participants meeting the categorical criteria will be presented in accordance with the Clinical Data Interchange Standards Consortium and Pfizer Standards (CaPS).

5.2.2. Analyses for Continuous Endpoints

For continuous variables, the data will be summarized using the number of participants, mean, median, standard deviation (SD), minimum, and maximum in accordance with the CaPS. For appropriate PK parameters, geometric mean and geometric coefficient of variation (%CV) will also be summarized.

5.3. Methods to Manage Missing Data

5.3.1. PK Concentrations

Methods to handle missing PK data are described below.

Concentrations Below the Limit of Quantification:

In all data presentations (except listings), concentrations below the limit of quantification (BLQ) will be set to zero. (In listings BLQ values will be reported as “<LLQ” where LLQ will be replaced with the value for the lower limit of quantification.).

Deviations, Missing Concentrations and Anomalous Values:

In summary tables and plots of median profiles, statistics will be calculated having set concentrations to missing if one of the following cases is true:

1. A concentration has been collected as ND (i.e., not done) or NS (i.e., no sample).
2. A deviation in sampling time (time deviation > 20%) is of sufficient concern or a concentration has been flagged as anomalous by the pharmacokineticist.

Note that summary statistics will not be presented at a particular time point if more than 50% of the data are missing.

An anomalous concentration value is one that, after verification of bioanalytical validity, is grossly inconsistent with other concentration data from the same individual or from other participants. For example, a BLQ concentration that is between quantifiable values from the same dose is considered as anomalous. Anomalous concentration values may be excluded from PK analysis at the discretion of the PK analyst or pharmacokineticist.

